## Methods

### *Inclusion criteria*

Healthy male players aged between 12 and 16 years old systematically ( $\geq 4$  times per week) participating in training and games will be eligible for inclusion.

### *Exclusion criteria*

- (1) musculoskeletal injury and/or neurological disorder that would affect strength and/or athletic performance testing, and/or the exercise execution.
- (2) adductor muscle injury within 6 months before study initiation.
- (3) pain greater than 2/10 on a Numeric Rating Scale (NRS) during strength and/or athletic performance testing, and/or during the intervention.
- (4) any systematic strength training of the adductor muscles during the last month prior to study initiation.

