### *Randomization*

Randomization will be performed before baseline testing with the use of an online software (<https://randomizer.org/>) by a person that will not otherwise be involved in the study. The randomization result for each participant will be placed in a numbered sealed opaque envelope and be given to the physiotherapist and the exercise therapist who will supervise the intervention. The group allocation will be announced to every participant the day of the first exercise session.

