### *Blinding*

The strength and athletic performance testing will be performed by a physiotherapist and an exercise therapist, respectively. They will not participate in the intervention supervision and will be unaware of the group allocation. The physiotherapist and the exercise therapist who will supervise the intervention, as well as the participants, will not be aware of the testing results until the completion of the study.

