### *Training groups*

The participants will be assigned to either a dynamic (DCA) or an isometric (ICA) Copenhagen Adduction exercise group and will perform a progressive exercise protocol for 6 weeks during

the in-season of the team at the club's training facilities. Both exercises will be performed twice per week with a 48-hour rest between them.

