#### *Outcome measures*

The primary outcome measures will be maximal eccentric (EHAD) and isometric (IHAD) hip adduction torque. The secondary outcome measures will be jump (squat jump, countermovement jump, countermovement jump with arm swing) and sprint (5m, 10m, 20m) capacity, delayed onset muscle soreness (DOMS), and perceived exertion. Torque will be

measured using a digital handheld dynamometer (Activforce 2, ActivBody, California, USA) and standardized strength testing (unilateral supine eccentric adduction strength test, unilateral supine isometric adduction strength test). Jump and sprint capacity will be measured using the Microgate Optogait (Microgate, Bolzano, Italy) and Fitlight System (Fitlight USA Inc., Miami, Florida), respectively. Perceived exertion will be recorded for each exercise using the Borg CR10 scale. DOMS will be recorded before the start of each exercise session, referring to the previous session, with the use of a numerical ranking scale (0-10).

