#### *Statistical analysis*

Statistical analysis will be performed using SPSS Statistics (v26, IBM Corporation). Baseline and follow-up values will be presented as mean  $\pm$  standard deviation (SD). For torque, jump, and sprint analysis, the highest value will be used. One-way ANCOVA will be used for between-group differences on the dependent variables (EHAD, IHAD, jump, sprint), while paired samples t-test will be used to determine the difference between baseline and follow-up values for the dependent variables (EHAD, IHAD, jump, sprint). Repeated measures ANOVA with Bonferroni correction will be used to determine the difference between groups for DOMS and perceived exertion. Athletes with compliance less than 75% of the total number of sessions will be excluded from the statistical analysis. Effect size (Cohen's d) is calculated will be set as small (0.2), moderate (0.5), and large (0.8), while statistical significance as  $p \leq 0.05$ .

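### The pain exclusion reaches past randomisation to events the assigned exercise can cause, and the plan does not say whether those players stay in the between-arm ANCOVA

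*Combined protocol and SAP*

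**What the plan says.** The Exclusion criteria section lists, as item (3), "pain greater than 2/10 on a Numeric Rating Scale (NRS) during strength and/or athletic performance testing, and/or during the intervention". It sets no time limit on the testing clause, so as worded it covers follow-up as well as baseline testing.

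On timing, the Randomization section states: "Randomization will be performed before baseline testing with the use of an online software". It adds: "The group allocation will be announced to every participant the day of the first exercise session". The Blinding section says of the testers: "They will not participate in the intervention supervision and will be unaware of the group allocation".

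On analysis, the Statistical analysis section states: "One-way ANCOVA will be used for between-group differences on the dependent variables (EHAD, IHAD, jump, sprint"). Its one rule on who is analysed is: "Athletes with compliance less than 75% of the total number of sessions will be excluded from the statistical analysis". It names no as-randomised set and no method for missing follow-up values, and it does not mention criterion (3).

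The schedule runs for 6 weeks: "Both exercises will be performed twice per week with a 48-hour rest between them". Among the outcomes, "DOMS will be recorded before the start of each exercise session, referring to the previous session", and exertion is scored on the Borg CR10 scale. Pain during the exercise itself is not among the listed measurements.

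**The concern.** Pain during the intervention cannot be a screening condition. It arises after the player has been randomised and has started his assigned exercise. The same holds for pain at follow-up testing. Both can be consequences of the exercise, and the two exercises differ: DCA has a 3-second eccentric phase, while ICA is a hold progressed partly by lever. The plan itself compares soreness and exertion between arms, so it treats unequal tolerance as an open question.

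If players leave the comparison because of such pain, the torque ANCOVA is conditioned on something that treatment can affect. Should removal differ by arm and be linked to strength gain, the players who remain are no longer comparable, and part of the estimated difference is selection. Adjusting for baseline torque balances starting strength. It does not restore comparability on how players responded.

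**Working it through.** **Step 1: when the pain can occur, and which text then applies.** Sessions planned: 6 weeks x 2 = 12.

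| Pain occurs at | Can the assigned exercise cause it? | Does the 75% rule also remove the player? |
|---|---|---|
| Baseline testing | No; no session has taken place and allocation is not yet announced | Not relevant |
| Sessions 1 to 8, player stops | Yes | Yes: at most 8/12 = 66.7% |
| Sessions 9 to 12, player stops | Yes | Not if no other session was missed: 9/12 = 75.0%, 10/12 = 83.3%, 11/12 = 91.7%, 12/12 = 100% |
| Follow-up testing | Yes | Not on account of the pain; attendance can be 100% |

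All four rows come after randomisation. In the second row two rules overlap. In the last two rows criterion (3) points to exclusion, while the Statistical analysis section, read alone, gives no ground for it.

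**Step 2: size, as an illustration only.** The plan gives no sample size, SD, pain rate or correlation, so there is no figure of its own to reproduce. Assumptions: no true difference between arms; pain tendency and baseline-adjusted gain are bivariate normal with correlation rho; the fraction p with the highest pain tendency is removed from each arm.

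The mean gain of those retained shifts by -rho x L(p), where L(p) = phi(z)/(1 - p) and z is the (1 - p) normal quantile.

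- L(0.05) = 0.1086; L(0.15) = 0.2743; L(0.25) = 0.4237.
- 5% v 15%, same rho in both arms: (0.2743 - 0.1086) x |rho| = 0.1657 x |rho|, which is 0.050 SD at 0.3 and 0.083 SD at 0.5.
- 5% v 25%: 0.3151 x |rho|, which is 0.095 to 0.158 SD. Nothing in the documents supports a gap this wide; it marks how the result scales.
- 15% in both arms, |rho| 0.5 in one and 0 in the other: 0.5 x 0.2743 = 0.137 SD.
- Equal rates with equal rho, or rho = 0: zero.

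**Step 3: does baseline adjustment remove it?** A simulated ANCOVA (2 million players per arm before exclusion, follow-up = 0.8 x baseline + gain, no true effect) gave these coefficients, arm B minus arm A:

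- A 5%, B 15%, rho = -0.3: +0.049.
- A 5%, B 25%, rho = -0.5: +0.158; with rho = +0.5: -0.158.
- A 25%, B 5%, rho = -0.5: -0.157.
- Both 15%, rho = -0.5: 0.002.
- A 5%, B 25%, rho = 0: 0.000.

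These agree with the formula. Adjustment leaves the bias in place, and its sign depends on the sign of rho and on which arm loses more players.

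**The case against.** The strongest objection is that the plan never says these players leave the analysis. The Exclusion criteria section governs participation. The only sentence that removes anyone from analysis is the compliance rule, and a player with late pain and 75% or more attendance does not meet it. This stands in part: a reader might infer that removal from the ANCOVA is the stated plan, and the documents do not go that far. It does not dispose of the point. Exclusion is the natural sense of an exclusion criterion, no text keeps the player in, and an unstated choice could be made after results are known.

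A second objection is that the effect may be small or absent. This also stands. Entry is limited to healthy players without recent adductor injury, and the plan tries to match repetitions and time under load. If 10% are removed in one arm and almost none in the other, with a correlation of size 0.3, the shift is 0.058 SD. For an assumed 20 to 50 randomised per arm, the two-sided type I error (normal approximation at 0.05) is then 0.054 to 0.059. The assumed rates also cover all removal for pain, so they overlap with the 75% rule and do not isolate what criterion (3) adds. A reader might infer that the trial result will be biased by a known amount; the documents support only that it can be.

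A reader might also infer that losing players to baseline-test pain after randomisation biases the arms. It should not: allocation has not been announced, the testers do not know it, and no exercise has been done. That loss costs numbers and chance balance. Blinded testers likewise limit discretionary exclusion at follow-up, though not pain that the exercise has caused.

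Finally, criterion (3) is the only rule in the text on pain during exercise. Narrowing it to solve an analysis problem would alter a clinical rule. That objection is right, and the remedy leaves the criterion's clinical content alone.

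**Conclusion.** The concern holds as a gap between two sections. Criterion (3) creates an exclusion after randomisation that the assigned exercise can trigger, and the Statistical analysis section does not settle whether such players are analysed. Bias in the between-arm ANCOVA requires removal that is related to gain and that differs between arms in rate or in that relation; otherwise there is none. Size and direction cannot be derived from the documents. The figure of about 0.05 to 0.08 SD of gain rests wholly on the assumed 5% v 15% exclusions, a correlation of size 0.3 to 0.5 and the normal model. It is not set against the plan's small effect of 0.2, because the plan does not say which SD standardises Cohen's d. This should be fixed before follow-up data are seen; confidence is medium, because removal from analysis is inferred.

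**What to change.** Confine the change to the analysis.

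1. State in the Statistical analysis section that the primary between-group ANCOVA includes all randomised players in their assigned arm, whatever their pain after randomisation or their attendance. Seek follow-up testing wherever the player is able. Name a method for missing follow-up values, for example multiple imputation within arm from baseline torque, sessions attended and recorded pain.
2. Keep the set without players who had pain above 2/10 and without those below 75% attendance as a sensitivity analysis.
3. Report by arm how many players had such pain, and when (which session, or follow-up testing).
4. If soreness and exertion scores up to the point of stopping are to be used, analyse them with a mixed model. A standard repeated measures ANOVA drops players with an incomplete series, so keeping the scores would not by itself help.
5. Reconcile the Exclusion criteria and Statistical analysis sections so that the eligibility, participation and analysis roles of criterion (3) are separate. No view is taken on when a player should stop the exercise.

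Confirming eligibility at baseline testing before randomising is an optional, separate change. It is feasible, since allocation is announced only on the first session day.

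Costs: pain during sessions becomes a new recorded item; some follow-up torque values may be limited by pain, so the primary result is the effect of assignment; imputation and mixed models bring their own assumptions about missing data; and the approved and registered wording must be amended.

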### *Ethics*

Ethical approval was obtained from University of West Attica ethics committee (60372/01-07-2025) and all players gave their written informed consent prior to inclusion in accordance with the Declaration of Helsinki. The research was prospectively registered to ClinicalTrials.gov (<https://clinicaltrials.gov/>).

### *Randomization*

Randomization will be performed before baseline testing with the use of an online software (<https://randomizer.org/>) by a person that will not otherwise be involved in the study. The randomization result for each participant will be placed in a numbered sealed opaque envelope and be given to the physiotherapist and the exercise therapist who will supervise the intervention. The group allocation will be announced to every participant the day of the first exercise session.

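### Randomisation precedes the baseline tests on which one exclusion criterion depends, creating avoidable post-randomisation exclusions and an allocation that exists before effort-dependent baseline torque is measured

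*Combined protocol and SAP*

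**What the plan says.** The Randomization section fixes the order: "Randomization will be performed before baseline testing with the use of an online software". The draw is made by someone otherwise outside the study. Each participant's result "will be placed in a numbered sealed opaque envelope and be given to the physiotherapist and the exercise therapist who will supervise the intervention". No time is given for the handover or for opening the envelopes. On disclosure to players the section says: "The group allocation will be announced to every participant the day of the first exercise session".

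Under Exclusion criteria, item 3 is "pain greater than 2/10 on a Numeric Rating Scale (NRS) during strength and/or athletic performance testing, and/or during the intervention". It does not say whether the testing meant is baseline, follow-up or both, and no separate screening test is described.

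The Blinding section says of the testers: "They will not participate in the intervention supervision and will be unaware of the group allocation". It keeps supervisors and participants from the test results until the study ends. It does not say whether supervisors are unaware of allocation while baseline testing is under way.

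The Statistical analysis section plans paired t-tests of baseline against follow-up and, between groups, "One-way ANCOVA will be used for between-group differences on the dependent variables (EHAD, IHAD, jump, sprint"). The covariate is not named. The only stated exclusion from analysis is attendance below 75% of sessions. There is no rule for a player who is randomised and then found ineligible.

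**The concern.** Eligibility should be settled before allocation. Here one criterion is observed during testing, and testing follows the draw. A player who fails it at baseline is a randomised participant who never starts, when he could have been a screening failure who was never randomised.

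Three things are at stake:

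- **Participant flow.** Such players appear as post-randomisation exclusions. Without a rule of their own, they cannot be told apart from players who did not adhere.
- **Analysis.** A player stopped at baseline may have no usable baseline measurement. He then cannot enter the paired t-tests, nor the ANCOVA if it adjusts for baseline.
- **Concealment.** Both primary outcomes are maximal hip adduction torque, which depends on effort and encouragement. An allocation that already exists when baseline torque is measured can in principle become known. One not yet drawn cannot.

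**Working it through.** **Sequence.** Set side by side, the sections give this order:

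1. The allocation is drawn and sealed (Randomization).
2. Baseline strength and performance are tested; pain above 2/10 excludes (Exclusion criteria, item 3, read as covering baseline).
3. The player learns his arm on the day of the first session (Randomization).

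No stated step between 1 and 3 uses the allocation.

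**What the analysis rule does with a baseline failure.** Training groups gives 6 weeks at 2 sessions per week, so 6 × 2 = 12 sessions, and 75% of 12 is 9. A player stopped at baseline attends 0 of 12 (0%), so he falls under the compliance exclusion although he was never given the chance to comply.

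**Size of the chance imbalance.** The available text gives no sample size, allocation ratio or expected exclusion rate, so there is no figure of the plan's own to reproduce. The inputs below are assumptions: n players per arm at randomisation (10, 20 or 30), and exclusion probability q (2% to 20%) that does not depend on arm. The remaining arm sizes a and b are then independent Binomial(n, 1 − q).

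The variance of a difference in means is proportional to 1/a + 1/b = (a + b)/(ab). An equal split of the same total gives 4/(a + b). Relative efficiency is therefore 4ab/(a + b)².

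| n per arm | q | Expected difference in arm size | P(difference ≥ 4) | Mean relative efficiency |
|---|---|---|---|---|
| 10 | 2% | 0.33 | 0.0% | 99.9% |
| 10 | 10% | 1.00 | 1.0% | 99.4% |
| 10 | 20% | 1.39 | 4.8% | 98.6% |
| 20 | 2% | 0.57 | 0.1% | 99.95% |
| 20 | 10% | 1.47 | 6.3% | 99.7% |
| 20 | 20% | 1.99 | 16.4% | 99.3% |
| 30 | 2% | 0.76 | 0.3% | 99.96% |
| 30 | 10% | 1.82 | 12.8% | 99.8% |
| 30 | 20% | 2.45 | 25.6% | 99.6% |

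The worst mean efficiency is 98.6%, a loss of 100 − 98.6 = 1.4%.

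**A concrete case.** Take 20 per arm and exactly 4 baseline failures (10% of 40). The split of the failures is hypergeometric, with C(40,4) = 91,390 possible sets.

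- 2:2 has probability C(20,2)²/91,390 = 190²/91,390 = 39.5%. The arms stay equal at 18 and 18.
- 3:1 either way has probability 2 × 1,140 × 20/91,390 = 49.9%. The arms become 17 and 19, with efficiency 4 × 17 × 19/36² = 1,292/1,296 = 99.7%.
- 4:0 either way has probability 2 × 4,845/91,390 = 10.6%. The arms become 16 and 20, with efficiency 4 × 16 × 20/36² = 1,280/1,296 = 98.8%.

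Arms are thus unequal in about 60% of such trials, usually by two players.

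**What reordering does and does not do.** If the draw follows baseline testing, this criterion causes no exclusions between randomisation and the first session. It does not by itself equalise the arms. On allocation the plan says only: "The participants will be assigned to either a dynamic (DCA) or an isometric (ICA) Copenhagen Adduction exercise group". With simple 1:1 randomisation of an assumed 40 eligible players, the expected difference is 5.0 and P(difference ≥ 4) is 64%.

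**The case against.** The strongest reply is that nothing here biases the comparison. Testers do not know the allocation, players do not know it until the first session, and the envelopes are sealed and opaque. Baseline exclusions should then be unrelated to arm. The same ineligible players leave under either order, so the analysable number is unchanged unless they are replaced. The efficiency cost of unequal arms is negligible, and the sponsor may have an unstated practical reason for drawing early.

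Most of this stands, and it rules out several stronger readings that a reader might infer:

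- **That balance between arms is lost.** No ratio or blocking is described, so no guaranteed balance exists to be lost, and the chance differences are small. A figure of about 60% unequal sounds large only because it counts a 17:19 split.
- **That concealment is broken.** The documents describe sealed, numbered envelopes. They do not say that the supervisors hold or have opened them during baseline testing. The exposure is a gap in the description, not evidence of a breach.
- **That criterion 1 also depends on testing.** It covers "musculoskeletal injury and/or neurological disorder that would affect strength and/or athletic performance testing, and/or the exercise execution". That wording looks ahead and can be settled from history before any test. The point rests on criterion 3.
- **That the ANCOVA necessarily loses these players.** This is so only if it adjusts for baseline, which is plausible but not stated.

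What the reply does not answer is that the exclusions are avoidable, that no rule handles or reports them, and that no stated step needs the allocation so early.

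**Conclusion.** The point holds as an avoidable weakness of sequence and reporting, not as a demonstrated bias. It assumes that criterion 3 covers baseline testing, as an eligibility criterion naturally would, and that no undescribed screening test comes first. Its statistical size is small: on average under about 1.5% of efficiency beyond the loss of the excluded players themselves, over the assumed range and with envelopes kept sealed. The stronger reasons to act are qualitative. Screening failures would be counted as randomised non-compliers, and an allocation nobody yet needs exists while effort-dependent baseline torque is measured.

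Criterion 3 also reaches pain during the intervention, and the 75% rule acts after treatment starts. Both can depend on arm and matter more for bias. They are separate questions, which reordering does not resolve.

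**What to change.** In the Randomization section, replace the timing of the draw with: after baseline testing is complete and eligibility is confirmed, and before the first exercise session. The independent person, the software and the sealed envelopes stay as they are. The section should also state when envelopes are handed over and opened, and the allocation ratio and any blocking, since reordering alone does not give equal arms.

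If allocation has already taken place, keep every randomised player in the flow diagram and report baseline-testing exclusions by arm, separately from non-compliance.

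The cost is a small change of wording. The one practical downside is that the draw must be scheduled between the end of baseline testing and the first session.

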### *Blinding*

The strength and athletic performance testing will be performed by a physiotherapist and an exercise therapist, respectively. They will not participate in the intervention supervision and will be unaware of the group allocation. The physiotherapist and the exercise therapist who will supervise the intervention, as well as the participants, will not be aware of the testing results until the completion of the study.

### *Training groups*

The participants will be assigned to either a dynamic (DCA) or an isometric (ICA) Copenhagen Adduction exercise group and will perform a progressive exercise protocol for 6 weeks during

the in-season of the team at the club's training facilities. Both exercises will be performed twice per week with a 48-hour rest between them.

